9.2 Disease Parameters

Measurable disease. Measurable lesions are defined as those that can be accurately measured in at least one dimension (longest diameter to be recorded) as \geq 20 mm by chest x-ray, as \geq 10 mm with CT scan, or \geq 10 mm with calipers by clinical exam. All tumor measurements must be recorded in millimeters (or decimal fractions of centimeters).

Note: Tumor lesions that are situated in a previously irradiated area are not considered measurable.

Malignant lymph nodes. To be considered pathologically enlarged and measurable, a lymph node must be \geq 15 mm in short axis when assessed by CT scan (CT scan slice thickness recommended to be no greater than 5 mm). At baseline and in follow-up, only the short axis will be measured and followed.

Non-measurable disease. All other lesions (or sites of disease), including small lesions (longest diameter <10 mm or pathological lymph nodes with \ge 10 to <15 mm short axis), are considered non-measurable disease. Bone lesions, leptomeningeal disease, ascites, pleural/pericardial effusions, lymphangitis cutis/pulmonitis, inflammatory breast disease, and abdominal masses (not followed by CT or MRI), are considered as non-measurable.

Note: Cystic lesions that meet the criteria for radiographically defined simple cysts should not be considered as malignant lesions (neither measurable nor non-measurable) since they are, by definition, simple cysts.

'Cystic lesions' thought to represent cystic metastases can be considered as measurable lesions, if they meet the definition of measurability described above. However, if non-cystic lesions are present in the same patient, these are preferred for selection as target lesions. Target lesions. All measurable lesions up to a maximum of 2 lesions per organ and 5 lesions in total, representative of all involved organs, should be identified as **target lesions** and recorded

and measured at baseline. Target lesions should be selected on the basis of their size (lesions with the longest diameter), be representative of all involved organs, but in addition should be those that lend themselves to reproducible repeated measurements. It may be the case that, on occasion, the largest lesion does not lend itself to reproducible measurement in which circumstance the next largest lesion which can be measured reproducibly should be selected. A sum of the diameters (longest for non-nodal lesions, short axis for nodal lesions) for all target lesions will be calculated and reported as the baseline sum diameters. If lymph nodes are to be included in the sum, then only the short axis is added into the sum. The baseline sum diameters will be used as reference to further characterize any objective tumor regression in the measurable dimension of the disease.

Non-target lesions. All other lesions (or sites of disease) including any measurable lesions over and above the 5 target lesions should be identified as **non-target lesions** and should also be recorded at baseline. Measurements of these lesions are not required, but the presence, absence, or in rare cases unequivocal progression of each should be noted throughout followup.

9.3 Methods for Evaluation of Measurable Disease

All measurements should be taken and recorded in metric notation using a ruler or calipers. All baseline evaluations should be performed as closely as possible to the beginning of treatment and never more than 4 weeks before the beginning of the treatment.

Clinical lesions. Clinical lesions will only be considered measurable when they are superficial (e.g., skin nodules and palpable lymph nodes) and ≥ 10 mm diameter as assessed using calipers (e.g., skin nodules). In the case of skin lesions, documentation by color photography, including a ruler to estimate the size of the lesion, is recommended.

Chest x-ray. Lesions on chest x-ray are acceptable as measurable lesions when they are clearly defined and surrounded by aerated lung. However, CT is preferable.

Conventional CT and MRI. This guideline has defined measurability of lesions on CT scan based on the assumption that CT slice thickness is 5 mm or less. If CT scans have slice thickness greater than 5 mm, the minimum size for a measurable lesion should be twice the slice thickness. MRI is also acceptable in certain situations (e.g. for body scans).

9.4 Response Criteria

9.4.1 Evaluation of Target Lesions

Complete Response (CR): Disappearance of all target lesions. Any pathological lymph nodes (whether target or non-target) must have reduction in short axis to <10 mm.

Partial Response (PR): At least a 30% decrease in the sum of the diameters of target lesions, taking as reference the baseline sum diameters

Progressive Disease (PD): At least a 20% increase in the sum of the diameters of target lesions, taking as reference the smallest sum on study (this includes the baseline sum if that is the smallest on study). In addition to the relative increase of 20%, the sum must also demonstrate an absolute increase of at least 5 mm. (Note: the appearance of one or more new lesions is also considered progressions).

Stable Disease (SD): Neither sufficient shrinkage to qualify for PR nor sufficient increase to qualify for PD, taking as reference the smallest sum diameters while on study

9.4.2 Evaluation of Non-Target Lesions

Complete Response (CR) Disappearance of all non-target lesions and normalization of tumor marker level. All lymph nodes must be non-pathological in size (<10 mm short axis) Note: If tumor markers are initially above the upper normal limit, they must normalize for a patient to be considered in complete clinical response.

Non-CR/Non-PD: Persistence of one or more non-target lesion(s) and/or maintenance of tumor marker level above the normal limits

Progressive Disease (PD): Appearance of one or more new lesions and/or *unequivocal progression* of existing non-target lesions. *Unequivocal progression* should not normally trump target lesion status. It must be representative of overall disease status change, not a single lesion increase.

Although a clear progression of "non-target" lesions only is exceptional, the opinion of the treating physician should prevail in such circumstances, and the progression status should be confirmed at a later time by the review panel (or Principal Investigator).

9.4.3 Evaluation of Best Overall Response

The best overall response is the best response recorded from the start of the treatment until disease progression/recurrence (taking as reference for progressive disease the smallest measurements recorded since the treatment started). The patient's best response assignment will depend on the achievement of both measurement and confirmation criteria.

Target Lesions	Non-Target Lesions	New Lesions	Overall Response	Best Overall Response when Confirmation is Required*
CR	CR	No	CR	> 4 wks. Confirmation**
CR	Non-CR / Non-PD	No	PR	
CR	Not evaluated	No	PR	>4 wks. Confirmation**
PR	Non-CR / Non-PD / not evaluated	No	PR	
SD	Non-CR / Non- PD/not evaluated	No	SD	documented at least once > 4 wks. from baseline**
PD	Any	Yes or No	PD	
Any	PD***	Yes or No	PD	no prior SD, PR or CR
Any	Any	Yes	PD	

Table 8 Determination of Best Overall Response

* See RECIST 1.1 manuscript for further details on what is evidence of a new lesion.

** Only for non-randomized trials with response as primary endpoint.

*** In exceptional circumstances, unequivocal progression in non-target lesions may be accepted as disease progression.

Note: Patients with a global deterioration of health status requiring discontinuation of treatment without objective evidence of disease progression at that time should be reported as "*symptomatic deterioration*." Every effort should be made to document the objective progression even after discontinuation of treatment.

9.4.4 Duration of Response

Duration of overall response: The duration of overall response is measured from the time measurement criteria are met for CR or PR (whichever is first recorded) until the first date that recurrent or progressive disease is objectively documented (taking as reference for progressive disease the smallest measurements recorded since the treatment started).

The duration of overall CR is measured from the time measurement criteria are first met for CR until the first date that progressive disease is objectively documented.

Duration of stable disease: Stable disease is measured from the start of the treatment until the criteria for progression are met, taking as reference the smallest measurements recorded since the treatment started, including the baseline measurements.

9.4.5 Progression-Free Survival

PFS is defined as the duration of time from start of treatment to time of first progression, death due to any cause or last patient contact alive and progression-free. In patients treated beyond progression, time to first progression (isolated) and second progression (multifocal) will be recorded.

9.4.6 Overall Survival

OS is defined as the duration of time from start of treatment to time of death due to any cause or last patient contact alive.

9.4.7 Off treatment/Off Study

Each subject has the right to withdraw from the study at any time without prejudice. The investigator may discontinue any subject's participation for any reason, including adverse event or failure to comply with the protocol. Should a subject withdraw from the study, the reason(s) must be stated on the case report form, and a final evaluation of the subject should be performed. Reasons for withdrawal from treatment include the following:

Progression of Disease: Remove patient from protocol therapy at the time progressive disease is documented.

Extraordinary Medical Circumstance: If at any time the treating physician feels constraints of this protocol are detrimental to the patient's health remove the patient from protocol therapy.

Patient's refusal to continue treatment: In this event, document the reason(s) for withdrawal.

Failure to comply with protocol (as judged by the investigator such as compliance below 80%, failure to maintain appointments, etc.).

Delay in treatment > 28 days due to toxicity

Patients may also be removed from the trial after completing all relevant trial related procedures.

10.0 ADVERSE EVENTS AND REPORTING

The timely reporting of adverse events (including toxic deaths) is required by the Food and Drug Administration. The reporting of toxicities is part of the data reporting for this study. The investigator is responsible for ensuring that all adverse events (AEs) and significant adverse

events (SAEs) that are observed or reported during the study, are collected and reported to the FDA, appropriate IRB(s), and Array in accordance with CFR 312.32 (IND Safety Reports).

10.1 Adverse Events

An *adverse event* (AE) is any symptom, sign, illness or experience that develops or worsens in severity during the course of the study. Intercurrent illnesses or injuries should be regarded as adverse events. Abnormal results of diagnostic procedures are considered to be adverse events if the abnormality:

- results in study withdrawal
- is associated with a serious adverse event
- is associated with clinical signs or symptoms
- leads to additional treatment or to further diagnostic tests is considered by the investigator to be of clinical significance

Adverse Event Reporting Period

The study period during which adverse events must be reported is defined as the period from the initiation of the first study treatment to 30 days following the last administration of study treatment.

Post-study Adverse Event.

All unresolved adverse events should be followed by the investigator until the events are resolved, the patient is lost to follow-up, or the adverse event is otherwise explained. At the last scheduled visit, the investigator should instruct each patient to report any subsequent event(s) that the patient, or the patient's personal physician, believes might reasonably be related to participation in this study.

Abnormal Laboratory Values.

A clinical laboratory abnormality should be documented as an adverse event if the abnormality is of a degree, typically at least grade 2 and not present as grade 1 or better at baseline, that requires active management; e.g. change of dose, discontinuation of the drug, more frequent follow-up assessments, further diagnostic investigation.

10.2 Recording of Adverse Events.

At each contact with the subject, the investigator must seek information on adverse events by specific questioning and, as appropriate, by examination. Information on all adverse events should be recorded immediately in the source document, and also in the appropriate adverse event module of the case report form (CRF). All clearly related signs, symptoms, and abnormal diagnostic procedures results should be recorded in the source document, though should be grouped under one diagnosis.

All adverse events occurring during the study period must be recorded. The clinical course of each event should be followed until resolution, stabilization, or until it has been determined that the study treatment or participation is not the cause. Serious adverse events that are still ongoing at the end of the study period must be followed up to determine the final outcome. Any serious adverse event that occurs after the study period and is considered to be at least possibly related to the study treatment or study participation should be recorded and reported immediately.

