1.0 OBJECTIVES

1.1 Primary Objectives

- To assess the clinical efficacy of HCQ + B by ORR.
- Determine the safety/tolerability of HCQ + B as measured by CTCAE 5.0.

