3.0 PATIENT SELECTION

3.1 Inclusion Criteria

Each subject must meet all of the following inclusion criteria to be enrolled in the study:

- 1) Metastatic or incurable NSCLC
- 2) Presence of a non-synonymous mutation in KRAS
- 3) Patient must have received at least one prior systemic therapy for metastatic NSCLC or be intolerant/ineligible/refuse available therapies with known benefit
- 4) Ability and willingness to sign a written informed consent document
- 5) Age ≥18 years old
- 6) At least one measureable lesion according to Response Evaluation Criteria in Solid Tumors (RECIST) 1.1
- 7) ECOG performance status 0-1

8) Adequate organ function, as defined below

System	Laboratory Value		
Hematological			
Absolute neutrophil count	>1.250/mcl		
(ANC)			
Platelets	≥100,000/mcL		
Hemoglobin	≥9 g/dL or ≥5.6 mmol/L		
Renal			
Serum creatinine OR	≤1.5 X upper limit of normal (ULN) OR		
Measured or calculated ^a			
creatinine clearance	≥50 mL/min for subject with creatinine levels >		
(GFR can also be used in place	1.5 X institutional ULN		
of creatinine or CrCl)			
Hepatic			
Serum total bilirubin	≤ 1.5 X ULN OR		
	Direct bilirubin ≤ ULN for subjects with total		
	bilirubin levels > 1.5 ULN		
	≤ 2.5 X ULN OR		
AST (SGOT) and ALT (SGPT)	≤ 5 X ULN for subjects with liver metastases		
^a Creatinine clearance should be calculated per institutional standard.			

- 9) Women of childbearing potential must have a negative serum pregnancy test performed within 72hours of the first dose of study therapy. Subjects of reproductive potential must agree to use acceptable birth control methods (see Appendix B for childbearing potential).
- 10) Qtc < 500 mSec on EKG
- 11) Must be able to swallow tablets
- 12) Must be willing to comply with protocol procedures (including completion of diaries and outcome measures

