11.5 Plans for Data Analysis

Primary

- The objective response rate and 95% exact confidence interval will be calculated.
- All observed toxicities will be graded and tabled (worse grade experienced in all cycles). The
 overall rate of > grade 3 toxicity and 95% exact confidence interval will be calculated.

Secondary

• Progression-free survival and overall survival will be estimated by the method of Kaplan and Meier. Median values and 95% confidence intervals will be calculated.

Exploratory

- Associations between objective response and expression of biomarkers pre-treatment will be tested using nonparametric Wilcoxon rank sum test. Comparisons of pre- and post-treatment biomarker expression will be conducted using Wilcoxon signed ranks test for paired data.
- Describe autophagic vesicles/cell in tumor tissue at various time points using descriptive statistics and scatter plots.
- To evaluate HCQ pharmacokinetics and pharmacodynamics to determine whether changes in blood-based autophagy biomarkers (ctDNA KRAS allelic frequency) reflect tissue-based changes in autophagy (autophagic vesicles/cell), the nonlinear mixed–effects modeling approach (NONMEM) will be used to perform a full population PK analysis. PK-PD analyses to be conducted by University of Sciences of Philadelphia. Analysis methods – See Section 18. The key variables for the population include the Cmax and half life. Population PK will be assessed and qualitatively compared to population PK findings from other HCQ studies. No hypothesis testing will be performed for any of the vairables.

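### The laboratory adverse-event rule in Section 10.1 is inverted as written and conflicts with the protocol's own adverse-event definition, so the primary grade 3-or-higher toxicity rate may be captured inconsistently and under-counted

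*Combined protocol and SAP*

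**What the plan says.** Safety is one of the two primary objectives in Section 1.1: "Determine the safety/tolerability of HCQ + B as measured by CTCAE 5.0". Section 11.5 gives the primary safety analysis. It plans a table, "All observed toxicities will be graded and tabled (worse grade experienced in all cycles", and one estimated rate: for toxicity at or above that level, the overall rate of "grade 3 toxicity and 95% exact confidence interval will be calculated". Section 11.5 does not say whether laboratory grades come from adverse-event forms or from the laboratory results themselves.

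Section 10.1 holds three rules that bear on a laboratory value:

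- **General definition.** An adverse event is "any symptom, sign, illness or experience that develops or worsens in severity during the course of the study".
- **Diagnostic results.** "Abnormal results of diagnostic procedures are considered to be adverse events if the abnormality" meets one of the listed triggers: withdrawal, association with a serious event, signs or symptoms, further treatment or tests, or clinical significance in the investigator's view. This rule has no grade or baseline condition.
- **Laboratory values.** The abnormality should be of a degree "typically at least grade 2 and not present as grade 1 or better at baseline, that requires active management". Examples of management follow: "e.g. change of dose, discontinuation of the drug, more frequent follow-up assessments, further diagnostic investigation".

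Section 10.2 requires every adverse event in the study period to be recorded. Section 10.3.5 makes a preexisting condition reportable when it gets worse.

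**The concern.** On the CTCAE scale, a grade better than 1 is grade 0. Requiring that the abnormality was not at grade 1 or better at baseline therefore requires a baseline of grade 2 or more. That is the reverse of a treatment-emergent rule. The entry criteria ask for adequate organ function, so the usual patient starts at or near normal and is the one the literal wording leaves out.

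The second condition, active management, ties recording to the investigator's response. Two patients with the same grade 3 value can be treated differently in the data because one was managed and the other was not.

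At stake is the grade 3-or-higher rate, the only safety estimate in Section 11.5 with a confidence interval. If laboratory grades reach it through adverse-event forms, the rate depends on which of the conflicting rules each form followed.

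**Working it through.** **Plan's own figure.** The documents state no expected value, target or threshold for the toxicity rate, so there is nothing to reproduce on this point. The response design in Section 11.4 does reproduce (type I error 0.047, power 0.805, early termination probability 0.736 against the stated 0.74) and is not affected.

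**Step 1. The baseline clause under three readings, for a value that reaches grade 3-4 on treatment.**

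| Reading | Baseline grade 0 | Baseline grade 1 | Baseline grade 2 |
|---|---|---|---|
| (a) Literal: was not grade 0-1 | left out | left out | kept |
| (b) *Better* meant as *higher*: was not grade 1 or above | kept | left out | left out |
| (c) Stray *not*: was grade 0-1 | kept | kept | left out |
| General definition: develops or worsens | kept | kept | kept |

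None of the three rows matches the last one. New events from a normal baseline are lost only under (a). Reading (c) is the probable intent, and it loses only worsening from grade 2.

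**Step 2. Do patients with abnormal baselines enter?** Yes. Section 3.1 accepts hemoglobin down to 9 g/dL and AST/ALT up to 2.5 × ULN, or "≤ 5 X ULN for subjects with liver metastases". The documents do not reproduce the CTCAE laboratory cut-offs, so I do not assign grades to these values.

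**Step 3. What the active-management condition removes.** Table 2 in Section 5.3 attaches a dose interruption or discontinuation to grade 3-4 AST/ALT (through its row for other reactions), to asymptomatic grade 4 CPK, and to the first occurrence of any other grade 3 or 4 reaction. These are changes of dose and so satisfy the condition. Among the laboratory events that Table 2 names, only asymptomatic grade 3 CPK has no action in its own row. Table 2 is also framed around treatment-related events, so it does not reach a value attributed to another cause.

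**Step 4. Size per missed patient.** Let x be the number of patients with any grade 3-or-higher event. Let m be the number of them whose only such event is an unrecorded laboratory event. The reported rate is (x − m)/n instead of x/n, so the loss is m/n.

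- n = 29 (full enrollment): 1/29 = 0.034, or 3.4 points per patient.
- n = 10 (stop after stage 1): 1/10 = 0.10, or 10 points per patient.

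The documents do not give m. As an assumed range, m = 0 to 3 at n = 29 gives a loss of 0 to 3/29 = 10.3 points.

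**Step 5. Are laboratory events common enough to matter?** Section 2.3.1 reports grade 3-4 creatine kinase elevation in 21% and 29% of two single-agent binimetinib populations. If those rates carried over (an assumption), 0.21 × 29 = 6.1 to 0.29 × 29 = 8.4 patients would be affected. This is not an estimate of m. The split between grades 3 and 4 is not given, grade 4 has a prescribed action, some of these patients will have another grade 3 event, and CPK is not in the chemistry panel of Section 8.0, footnote 10.

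**The case against.** The strongest reply is that other rules still catch these events. The general definition in Section 10.1 covers anything new or worse. The diagnostic-results rule has no baseline condition and includes clinical significance. Section 10.2 requires all adverse events to be recorded, and Section 10.3.5 covers worsening of a preexisting condition. The grade and baseline words are introduced as typical, so they are guidance and not a hard filter. Closer follow-up and further tests count as active management, so a value under heightened watch qualifies. Section 11.5 speaks of all observed toxicities and does not limit itself to recorded adverse events. The literal reading, under which only patients already at grade 2 would count, is implausible as an instruction.

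Most of this stands, and it rules out a stronger inference that a reader might draw: that new or worsened grade 3-4 laboratory toxicities simply drop out of the rate. The documents do not support that, because several routes to recording stay open.

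The reply does not remove the conflict. Calling the clause typical makes it discretionary without correcting its direction. An asymptomatic grade 3 value followed on the ordinary schedule, and not judged clinically significant, can fail both the laboratory rule and the diagnostic-results rule. Only the general definition would then bring it in, and the specific rule contradicts that definition.

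**Conclusion.** The concern holds as a conflict between recording rules. The baseline clause is inverted as written, no reading of it matches the general definition or Section 10.3.5, and the active-management condition makes capture depend on investigator action. The consequence is inconsistent capture and possible under-counting of the primary grade 3-or-higher rate. The clearest exposure is an asymptomatic grade 3 value with no prescribed action.

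The direct effect of a missed event is downward, at 3.4 points per patient at n = 29 or 10 points at n = 10. This assumes that laboratory grades reach the rate through adverse-event forms and that the missed patient has no other grade 3-or-higher event. The total cannot be derived from the documents.

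A reader might also infer that the trial's continuation or success decision is at risk. It is not: the rules in Section 11.4 use response only, and Section 11.5 attaches no threshold to the toxicity rate. The matter is worth correcting because safety is a primary objective and the correction is cheap.

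**What to change.** The change concerns recording and analysis only.

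- **Section 10.1.** Replace the baseline clause with wording to this effect: *A laboratory value is recorded as an adverse event if its CTCAE v5.0 grade is higher than at baseline and it meets a criterion listed in this section. Every post-baseline value of grade 3 or higher that exceeds the baseline grade is recorded whether or not it is managed.*
- **Section 11.5.** State that the laboratory part of the grade 3-or-higher rate is derived from the worst post-baseline grade of the blood counts and chemistry already collected under Section 8.0, graded against baseline, together with any other laboratory values recorded.

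The cost is about two sentences and a programmed grading of existing data, with no new visit or test. The reported rate may come out somewhat higher.

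One limit remains. CPK is not in the listed chemistry panel, so derivation from that panel will not capture it. The revised Section 10.1 wording covers CPK only where it is measured.
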